8. REGULATORY ISSUES	9
8.1 ETHICS APPROVAL	9
8.2 CONSENT	9
8.3 CONFIDENTIALITY	9
8.4 INDEMNITY	9
8.5 SPONSOR	9
8.6 AUDITS AND INSPECTIONS	9
9. STUDY MANAGEMENT	10
10. PUBLICATION POLICY	10
11. REFERENCES	10
APPENDIX 1. SCHEDULE OF ASSESSMENTS	12
APPENDIX 2. PARTICIPANT INFORMATION SHEET (PIS)	13
APPENDIX 3. PARTICIPANT INVITATION LETTER	18
APPENDIX 4. GP LETTER	20
APPENDIX 5. CONSENT FORM	22

GLOSSARY OF ABBREVIATIONS

SDB	Sleep Disordered Breathing
OSA	Obstructive sleep apnoea
CSA	Central sleep apnoea
HFpEF	Heart Failure with preserved ejection fraction
HFrEF	Heart Failure with reduced ejection fraction
AHI	Apnoea-hypopnoea index
LVEF	Left ventricular ejection fraction

STUDY SUMMARY

TITLE Prevalence and Prognosis of Heart Failure with Preserved Ejection Fraction (HFpEF) in patients assessed for Sleep Disordered Breathing (SDB)

DESIGN Prospective observational study

- AIMS**
1. To establish the prevalence of HFpEF among patients being investigated for SDB.
 2. To examine the type and severity of SDB in patients identified with HFpEF.
 3. To characterise the phenotype of the patients that are identified with HFpEF
 4. To determine the prognosis of patients with HFpEF based on hospitalisation and mortality data.

OUTCOME MEASURES Primary Outcome measure:

- 1) Number of patients with diagnostic criteria for HFpEF

Secondary outcome measures:

- 1) The number of patients with SDB and the proportion of OSA and CSA.
- 2) Apnoea-hypopnoea index (AHI) as an indicator of SDB severity.
- 3) The frequency of cardiac co-morbidities including hypertension, coronary artery disease, diabetes and atrial fibrillation.
- 4) Rate of hospitalisation and mortality over 12 months.

POPULATION Patients referred for respiratory polygraphy at the Royal Brompton Hospital

ELIGIBILITY Patients ≥ 40 years without pre-existing treated SDB or heart failure

DURATION 20 months

1. INTRODUCTION

1.1 BACKGROUND

Daytime somnolence, fatigue and feeling unrefreshed on waking are typical symptoms of sleep disordered breathing (SDB). Respiratory polygraphy, performed either in hospital or at home, readily allows confirmation of the diagnosis. Obstructive sleep apnoea (OSA) and central sleep apnoea (CSA) are two types of SDB. In OSA there is collapse of the pharynx leading to partial or complete airway obstruction, whilst in CSA there is abnormality in the neural brainstem control of breathing. Although the mechanisms of obstructive and central apnoea differ, they both result in repetitive reduction (hypopnoea) or cessation of breathing (apnoea). This in turn can cause sleep fragmentation, exaggerated negative intra-thoracic pressure swings, intermittent hypoxia and sympathetic nervous system activation, which can have detrimental effects on the cardiovascular system [1].

Whilst performing a respiratory polygraphy allows accurate diagnosis of SDB it does not address potential underlying cardiovascular disease in the same patient. It is well – established that SDB is common among patients with heart failure, both with reduced (HFrEF) and preserved ejection fraction (HFpEF) [2]. SDB may occur as a consequence of heart failure, but has also been implicated in its progression. Bitter et al studied SDB in patients with heart failure with normal ejection fraction identifying its prevalence in 69% of individuals [3]. Central sleep apnoea, which is principally linked with heart failure, is independently associated with a worse prognosis, including mortality.

Heart failure with preserved ejection fraction (HFpEF) accounts for up to half of all heart failure cases and is associated with significant morbidity and mortality [4]. It can be challenging to diagnose as it can present with non-specific symptoms, be obscured by concomitant diseases and there is a lack of a simplified diagnostic test. Unrecognised heart failure, predominately with preserved ejection fraction, was shown to be present in 1 in 6 primary care patients with breathlessness on exertion [5]. In 2016 the European Society of Cardiology (ESC) set out updated diagnostic criteria for HFpEF. This combined the signs and symptoms of heart failure, left ventricular ejection fraction (LVEF) $\geq 50\%$, elevated natriuretic peptide levels, and relevant structural disease or diastolic dysfunction [6].

The phenotype of patients with SDB and those with heart failure with preserved ejection fraction (HFpEF) share similar characteristics [7]. Increasing age, hypertension, obesity, diabetes mellitus and atrial fibrillation are well recognised links in both groups. It has been shown that in patients with similar co-existent diseases, the added presence of heart failure with preserved ejection fraction results in higher morbidity and mortality rates [8].

1.2 RATIONALE FOR CURRENT STUDY

Previous studies have evaluated the prevalence of SDB in patients known to have HFpEF, but not vice versa. Given the relationship between the two conditions and their similar phenotypes, we hypothesise that a subset of patients with unrecognised HFpEF can be identified in the population being investigated for SDB. We aim to determine the prevalence of patients with diagnostic criteria for HFpEF and examine the relationship with SDB. We will also collect prognostic data on hospitalisations and mortality over a 12 month period. This will allow inferences to be made as to whether this population should be targeted for screening for HFpEF.

2. STUDY OBJECTIVES

2.1 PRIMARY OBJECTIVE

- To identify patients with diagnostic criteria for HFpEF and establish the prevalence.

2.2 SECONDARY OBJECTIVES

- To examine the type and severity of SDB in patients identified with HFpEF.
- To characterise the phenotype of the patients that are identified with HFpEF.
- To determine the prognosis of patients with HFpEF based on hospitalisation and mortality data.

3. STUDY DESIGN

This is a prospective, observational study. The aim will be to recruit 155 patients and to collect prognostic data over a 12 month period from the participant's enrolment.

We will recruit patients referred for respiratory polygraphy, as part of their standard clinical care, at the Royal Brompton Hospital Sleep Centre. These patients would be symptomatic or be at moderate or high risk for SDB. Patients eligible will be ≥ 40 years with no history of pre-existing heart failure with reduced ejection fraction or treated sleep disordered breathing.

The patients will have a respiratory polygraphy (Embletta MPR) performed either in-hospital or at home as part of their usual care. The respiratory polygraphy involves recording nasal air flow, snore sensor, pulse oximetry, chest and abdominal movement. It is a validated for screening for sleep disordered breathing, distinguishing between obstructive sleep apnoea (OSA) and central sleep apnoea (CSA). Hypopnoea will be defined as a 30% reduction in airflow in combination with at least 3% oxygen desaturation. Apnoea will be defined as a cessation of airflow for >10 s, and in case of CSA without any thoracic or abdominal breathing effort. The apnoea-hypopnoea index (AHI) will be used to assess the severity of SDB with the following classification: Mild 5-14/h, moderate 15-30/h and severe >30 /h. Patients will be classified as OSA or CSA depending on the majority of events.

On attendance for respiratory polygraphy the following investigations will be performed:

1. Each patient will have documentation of their symptoms, medical diagnoses, medications and social history. A clinical cardiovascular examination will be performed.
2. Two symptom questionnaires will be completed. The Epworth Sleepiness questionnaire will assess daytime somnolence and is standard practice in SDB assessment. The SF-36 Questionnaire will assess indices of quality of life.
3. Biomarker assessment of heart failure will be performed by taking a single venous blood sample for plasma N-terminal-pro BNP (NT-proBNP) level and Growth Differentiation Factor-15 (GDF-15).
4. An electrocardiogram (ECG) will be carried out for documentation of cardiac rhythm.

5. Echocardiography will be performed for assessment of structural heart disease and diastolic function in accordance to standard techniques. Parameters assessed will include: Left ventricular ejection fraction (LVEF), left ventricular diastolic function (E/A, DT, E' septal, E' lateral, E/E'), left ventricular wall thickness/mass, left atrial size and right ventricular (RV) function.

The criteria for heart failure with preserved ejection fraction will be in accordance to European Society of Cardiology guidelines as set out: Presence of symptoms and/or signs of heart failure, LVEF \geq 50%, elevated levels of natriuretic peptides, and relevant structural disease or diastolic dysfunction.

All recruited patients will be contacted by telephone at 3 monthly intervals over the next 12 months. Information recorded will include symptoms, new diagnoses, medication changes and hospitalisations. Additional data from hospital records and GP records will be used to verify the number of hospitalisations, the reason for admission and the outcome. This method will also be used to collect mortality data and if required certification information will be sought from the General Register Office.

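### Does the OSA/CSA majority rule need a written convention for hypopnoeas before the type of SDB can be reported?

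*Combined protocol and SAP*

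**What the plan says.** Section 3 (Study Design) defines two kinds of respiratory event. For the first, "Hypopnoea will be defined as a 30% reduction in airflow in combination with at least 3% oxygen desaturation". For the second, "Apnoea will be defined as a cessation of airflow for >10 s, and in case of CSA without any thoracic or abdominal breathing effort". It then introduces the AHI as the measure of severity and closes with the typing rule, "Patients will be classified as OSA or CSA depending on the majority of events". The same section names a single polygraphy device, lists chest and abdominal movement among its signals, and describes the test as validated for telling obstructive from central apnoea. The recordings are "performed either in-hospital or at home as part of their usual care".

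The label feeds two places. Secondary outcome 1 in the Study Summary is "The number of patients with SDB and the proportion of OSA and CSA", and a secondary objective in section 2.2 is "To examine the type and severity of SDB in patients identified with HFpEF". Section 7 sets the sample size from HFpEF prevalence alone and does not mention the type of SDB.

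**The concern.** A majority rule needs every counted event to have a type. Apnoeas have one: effort is either absent or not. The hypopnoea definition uses airflow and desaturation only, and section 1.1 says that both forms of SDB produce hypopnoeas, so the background supplies no default either. If hypopnoeas are counted, a scorer could treat them all as obstructive because some effort is present, type them from the effort channels, or leave them untyped in the denominator. If they are not counted, that too is unwritten. There is no rule for ties.

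At stake is the OSA/CSA split, both in the cohort and among patients found to have HFpEF. The protocol links central apnoea principally with heart failure and with worse prognosis, so in this study the label carries clinical meaning. A convention chosen after the results were known would be a further worry.

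**Working it through.** **1. The plan's own figure.** Inputs from section 7: prevalence p = 0.10, half-width d = 0.05, 95% confidence (z = 1.96), 10% dropout.

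- n = z²p(1 − p)/d² = 1.96² × 0.10 × 0.90 / 0.05² = 138.3, rounded up to 139.
- 139 / 0.90 = 154.4, rounded up to 155.

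Both stated figures reproduce. Neither uses the OSA/CSA label. HFpEF is diagnosed from symptoms or signs, LVEF, natriuretic peptides and cardiac structure or diastolic function, with no sleep data. The AHI counts events whatever their type, so severity is unaffected too.

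**2. What the text settles.** The word for what is counted is left undefined in section 3. Two readings are open: all apnoeas and hypopnoeas, since both make up the AHI just mentioned; or only events that have been given a type, which on the written definitions means apnoeas. The no-effort test could also be applied literally to a hypopnoea, which would then be non-central whenever effort is present. So the document leaves the choice open, but it does not prescribe a rule that cannot be carried out.

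**3. Can the choice change a label?** Let c, o and h be central apnoeas, obstructive apnoeas and hypopnoeas. The recordings below are hypothetical; the documents give no event mix.

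| Recording (c, o, h) | Convention | Result |
|---|---|---|
| A (12, 3, 15) | apnoeas only | 12/15 = 80% central: CSA |
| A | hypopnoeas counted, untyped | 12/30 = 40% central, 3/30 = 10% obstructive: no majority |
| A | k hypopnoeas typed central | 12 + k against 18 − k: OSA for k ≤ 2, tie at k = 3, CSA for k ≥ 4 |
| B (6, 4, 20) | apnoeas only | 6/10 = 60% central: CSA |
| B | all hypopnoeas obstructive | 24/30 = 80% obstructive: OSA |
| C (12, 1, 8) | any of the above | 12/21 = 57% to 20/21 = 95% central when hypopnoeas are typed, 12/13 = 92% on apnoeas only: CSA |

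In general the label is the same under every convention when |c − o| > h. Recording C meets this (11 > 8); A (9 against 15) and B (2 against 20) do not. The effect can go either way: an obstructive default lowers the CSA share, and typing hypopnoeas as central raises it.

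**4. What one changed label is worth.**

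- Whole cohort (secondary outcome 1): 100/139 = 0.7 points if all have SDB; 100/69.5 = 1.4 points if half do (an assumed fraction).
- HFpEF patients: 139 × 0.10 = 13.9. Section 1.1 cites a study of heart failure with normal ejection fraction "identifying its prevalence in 69% of individuals" for SDB. Carrying that over as an assumption, 13.9 × 0.69 = 9.6, so 100/9.6 = 10.4 points. If all 13.9 have SDB, 100/13.9 = 7.2 points.
- Appendix 1 puts the sleep study at baseline, so later dropout need not reduce the number. With 155: 15.5 × 0.69 = 10.7, giving 100/10.7 = 9.3 points, or 100/15.5 = 6.5 points if all have SDB.

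These steps are 1/n. They would apply to any labelling error in groups of these sizes, and say nothing about how often this one would occur.

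**The case for a change.** The best case for a change is that it is cheap and the gap is plain. A few lines in section 3, written before scoring, would fix whether hypopnoeas count and how they are typed, using channels already recorded. They would remove any suspicion that the convention was picked afterwards and let an outside reader interpret the split. A validated device supplies signals, not a decision rule. Consistency within one centre does not tell readers which convention was used.

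Much of this stands as a remark on documentation. It falls short of showing that the split could not be reproduced. The documents give no sign of several scorers working to different conventions, and a convention applied consistently at one centre gives reproducible labels within the study. No link is shown between home or hospital recording and the typing of hypopnoeas. The silence of section 7 is no further defect, because the classification belongs in section 3. An exact tie over a whole recording is a marginal case. The proposed wording would also not select a convention on statistical grounds; it would ask the centre to write down whichever one it uses. That can equally be stated in the methods when results are reported.

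**Conclusion.** The observation is correct but does not warrant a change. Section 3 leaves open whether hypopnoeas count towards the majority and how they would be typed, so the OSA/CSA split rests on an unstated scoring convention. This is detail that the sleep centre can be expected to fill with its usual practice, using effort signals it already records. Nothing written in the plan is shown to give a wrong result.

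The reach is limited to descriptive secondary results. The primary outcome, the AHI severity classes and the sample size are untouched, and no test of OSA against CSA is specified. Each changed label is worth about 0.7 points in the cohort if all 139 have SDB, and about 7 to 10 points among HFpEF patients with SDB (down to 6.5 if all 155 are scored).

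The conclusion assumes that one convention is applied throughout. The HFpEF figures also assume the plan's 10% prevalence and an SDB share between 69% and 100%. How many recordings fail the |c − o| > h condition, and in which direction the split would move, cannot be known from the documents.

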4. PARTICIPANT ENTRY

4.1 INCLUSION CRITERIA

Patients aged \geq 40 years referred for a respiratory polygraphy at the Sleep Centre at the Royal Brompton Hospital.

4.2 EXCLUSION CRITERIA

Patients with known heart failure and those receiving treatment for pre-existing sleep disordered breathing.

5. ADVERSE EVENTS

5.1 DEFINITIONS

Adverse Event (AE): any untoward medical occurrence in a patient or clinical study subject.

Serious Adverse Event (SAE): any untoward and unexpected medical occurrence or effect that:

- Results in death
- Is life-threatening – *refers to an event in which the subject was at risk of death at the time of the event; it does not refer to an event which hypothetically might have caused death if it were more severe*
- Requires hospitalisation, or prolongation of existing inpatients' hospitalisation
- Results in persistent or significant disability or incapacity
- Is a congenital anomaly or birth defect

Important AEs that are not immediately life-threatening or do not result in death or hospitalisation but may jeopardise the subject or may require intervention to prevent one of the other outcomes listed in the definition above, will also be considered serious.

5.3 REPORTING PROCEDURES

All adverse events should be reported. Depending on the nature of the event the reporting procedures below should be followed. Any questions concerning adverse event reporting should be directed to the Chief Investigator in the first instance.

5.3.1 Non serious AEs

All such events, whether expected or not, should be recorded.

5.3.2 Serious AEs

An SAE form should be completed and faxed to the Chief Investigator within 24 hours. However, relapse and death due to pre-existing conditions, and hospitalisations for elective treatment of a pre-existing condition do not need reporting as SAEs.

All SAEs should be reported to the South Central-Oxford B REC where in the opinion of the Chief Investigator, the event was:

- 'related', i.e. resulted from the administration of any of the research procedures; and
- 'unexpected', i.e. an event that is not listed in the protocol as an expected occurrence

Reports of related and unexpected SAEs should be submitted within 15 days of the Chief Investigator becoming aware of the event, using the NRES SAE form for non-IMP studies. The Chief Investigator must also notify the Sponsor of all SAEs.

Local investigators should report any SAEs as required by their Local Research Ethics Committee, Sponsor and/or Research & Development Office.

Contact details for reporting SAEs

Please send SAE forms to:

**[name]
Imperial College London
National Heart & Lung Institute
[name]
London
[name]**

[contact], F.A.O. [name]

[contact] (Mon to Fri 09.00 – 17.00)

6. ASSESSMENT AND FOLLOW-UP

We will be conducting telephone calls at 3 monthly intervals following the patient's enrolment to collect information related to the patient's health and hospitalisation history. The patient's involvement in the study will be concluded following the final telephone contact at month 12.

Any cardiovascular findings requiring follow-up will be reported to the patient's usual clinical care team and General Practitioner.

The follow-up of patients from a sleep disordered breathing perspective will be directed by their usual clinical care team.

7. STATISTICS AND DATA ANALYSIS

The prevalence of HFpEF in this population has not previously been defined. In this study if we assume the prevalence of HFpEF to be 10% and if the precision of this estimate is within 5% then for a 95% confidence interval, the required sample size will be 139 subjects. Assuming a 10% drop out, we would require a final sample size of 155.

The primary outcome will be presented as a proportion. For the prognostic data, categorical data will be presented as frequency (percentage) and the survival pattern described using the log rank test and Kaplan-Meier survival plots.

Data and all appropriate documentation will be stored for a minimum of 10 years after the completion of the study, including the follow-up period.

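### Does the primary prevalence miss its 5-point precision because section 7 uses a normal-approximation sample size and attaches no interval to the result?

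*Combined protocol and SAP*

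**What the plan says.** Section 7 (Statistics and Data Analysis) acknowledges that the prevalence in this population is unknown and works from an assumption: "if we assume the prevalence of HFpEF to be 10"%. It continues that if "the precision of this estimate is within 5% then for a 95% confidence interval, the required sample size will be 139 subjects", which reads as a half-width of 5 percentage points with 95% confidence. It then adds: "Assuming a 10% drop out, we would require a final sample size of 155". Section 3 (Study Design) gives the same recruitment target of 155.

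On analysis, section 7 says of the primary result only this: "The primary outcome will be presented as a proportion". It names no confidence interval and no interval method. A 95% interval appears only in the sample-size sentence.

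Section 1.1 (Background) cites a figure from a different setting: unrecognised heart failure, mostly with preserved ejection fraction, "was shown to be present in 1 in 6 primary care patients with breathlessness on exertion".

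Appendix 1 places every test needed for the HFpEF criteria (history and examination, NT-proBNP, ECG, echocardiogram) at the baseline visit. Only telephone calls follow.

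**The concern.** Prevalence is the only primary objective, and section 1.2 wants it to inform whether this population should be screened for HFpEF. Three things look wrong together.

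- The figure 139 comes from the symmetric normal (Wald) formula. With about 14 expected cases, a Wald interval covers less than its nominal 95%, and it errs mostly by lying too low. An asymmetric interval reaches more than 5 points above the estimate.
- The analysis text drops the interval on which the study was sized. A bare proportion based on about 14 cases shows no uncertainty.
- The margin holds only if prevalence is near or below 10%. The 1 in 6 quoted in the background suggests it could be higher.

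If all this held, the main result would be reported with overstated precision, and the upper plausible prevalence, which bears on a screening argument, would be understated.

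**Working it through.** **Inputs.** From section 7: p = 0.10, half-width d = 0.05, 95% two-sided (z = 1.96), drop-out 10%. From section 1.1: 1 in 6 as an alternative prevalence.

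**1. Reproduce the plan's figures.**

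n = z² p(1 − p)/d² = 1.96² × 0.10 × 0.90 / 0.05² = 138.3, rounded up to 139.

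139 / (1 − 0.10) = 154.4, rounded up to 155.

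Both match. There is no arithmetic error.

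**2. Is 5 points delivered as a half-width?** Take the counts nearest 10%.

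| Observed | Method | 95% interval | Half-width (points) | Upper arm (points) |
|---|---|---|---|---|
| 14/139 | Wald | 5.1% to 15.1% | 5.00 | 5.0 |
| 14/139 | Wilson | 6.1% to 16.2% | 5.05 | 6.1 |
| 14/139 | Exact (Clopper-Pearson) | 5.6% to 16.3% | 5.35 | 6.2 |
| 16/155 | Wald | 5.5% to 15.1% | 4.79 | 4.8 |
| 16/155 | Wilson | 6.5% to 16.1% | 4.83 | 5.8 |
| 16/155 | Exact (Clopper-Pearson) | 6.0% to 16.2% | 5.10 | 5.9 |

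The smallest n giving a half-width of 5 points or less at p = 0.10 is 141 with Wilson and 158 with the exact interval, against the plan's 139. Holding the upper arm alone to 5 points would need 196 (Wilson) or 202 (exact), but section 7 does not set that target.

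**3. Coverage.** For a true prevalence of 10%, sum the binomial probabilities of all counts whose interval contains 0.10.

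| n | Method | Coverage | Interval wholly below truth | Interval wholly above truth |
|---|---|---|---|---|
| 139 | Wald | 93.3% | 5.6% | 1.1% |
| 139 | Wilson | 95.2% | 1.2% | 3.7% |
| 139 | Exact | 96.8% | 1.2% | 2.1% |
| 155 | Wald | 94.2% | 4.7% | 1.1% |
| 155 | Wilson | 94.1% | 2.3% | 3.6% |
| 155 | Exact | 95.6% | 2.3% | 2.1% |

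At n = 139 the Wald shortfall is 95 − 93.3 = 1.7 points. Averaged over true prevalences from 5% to 20%, Wald covers 93.7% (minimum 89.7%) and Wilson 95.1%.

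**4. Which n applies?** The HFpEF criteria are all assessed at baseline, so a participant lost during telephone follow-up still contributes to the prevalence. Unless baseline tests are missing, the evaluable number is nearer 155 than 139. At n = 155 and p = 0.10, Wilson gains nothing over Wald in total coverage, although its two tails are better balanced.

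**5. Chance of meeting the margin.** If the truth is 10% and n = 139, the probability of 13 or fewer cases (Wald half-width 4.84 points or less) is 47%. At 14 cases the half-width is 5.003 points, and counting that as 5 raises the probability to 58%. Odds near even are expected from any formula evaluated at the expected proportion, so this reveals no defect.

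**6. Prevalence of 1 in 6.** Half-width = 1.96 × √(0.1667 × 0.8333 / n), which is 6.2 points at n = 139 and 5.9 at n = 155. That is about one point wider than planned.

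**The case for a change.** The strongest case for acting is that section 7 is complete as it stands and contains no commitment to an interval for the sole primary result, in a study whose only statistical justification is the width of that interval. Naming Wilson or exact in advance would cost a sentence or two and no patients, and would prevent the method being chosen after the data are seen. Wald also errs on the side that matters for a screening argument: its misses fall below the truth in 5.6% of samples at n = 139 and in 4.7% at n = 155, so full retention does not remove the imbalance. And if prevalence were 1 in 6, no method would deliver 5 points.

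Some of this stands. The interval and its method are not stated, and the Wald imbalance is real. The rest carries less weight. Using a normal approximation for planning does not bind the analysis, so the under-coverage belongs to an interval the plan never chooses. Requiring the upper arm alone to stay within 5 points is stricter than the plan's own statement, which is most naturally a half-width. Freedom to choose a method afterwards matters little when the candidate upper limits at 14/139 run only from 15.1% to 16.3%. The 1 in 6 figure concerns breathless primary care patients and heart failure that is mostly, not solely, HFpEF. Section 7 is open that 10% is an assumption.

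**Conclusion.** No change is called for. The sample size is right for the formula used, and the stated precision, read as a half-width at 10% prevalence, is met to within 0.35 points by every interval considered at n = 139 and to within 0.10 points at n = 155. The Wald coverage loss at the planning value is 1.7 points at n = 139 and 0.8 at n = 155, and would arise only if analysts chose that interval.

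The silence about an interval is a gap that analysts fill sensibly. A single-group descriptive study sized on a 95% confidence interval would be expected to report one, no test or decision threshold depends on the method, and the count with its denominator lets any reader derive it. When the result is written up, a Wilson or exact interval is the natural choice, with those fully assessed at baseline as the denominator. At 10% prevalence it would run from roughly 6% to 16%.

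This conclusion rests on two readings: that the 5% is an absolute half-width, and that most recruited participants complete the baseline tests. If prevalence is nearer 1 in 6, the half-width grows to about 6 points; the reported interval would show this.

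### Must the plan name the log-rank groups, define the hospitalisation rate and promise confidence intervals before the prognosis aim can be analysed soundly?

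*Combined protocol and SAP*

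**What the plan says.** The prognosis aim is a secondary objective in section 2.2: "To determine the prognosis of patients with HFpEF based on hospitalisation and mortality data". The matching secondary outcome in the Study Summary is "Rate of hospitalisation and mortality over 12 months".

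Section 3 follows every recruited patient, not only those with HFpEF, and undertakes to "collect prognostic data over a 12 month period from the participant's enrolment". Telephone calls are made every three months. Hospital and GP records are then used to "verify the number of hospitalisations, the reason for admission and the outcome". Deaths are traced in the same way, with the General Register Office as a further source if needed. Section 6 fixes the end of follow-up: "The patient's involvement in the study will be concluded following the final telephone contact at month 12".

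The analysis text for this aim is one sentence in section 7: "categorical data will be presented as frequency (percentage) and the survival pattern described using the log rank test and Kaplan-Meier survival plots". The only confidence interval in that section belongs to the sample-size calculation for prevalence, which ends: "Assuming a 10% drop out, we would require a final sample size of 155".

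**The concern.** Three things look wrong at first.

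- **The log-rank test has no stated groups or event.** The test compares groups and yields no estimate, so it cannot by itself describe survival. HFpEF versus no HFpEF, obstructive versus central apnoea, or classes of apnoea-hypopnoea index would all fit the wording. So would death, first admission, or either. The choice could be made after the data are seen.
- **No interval is planned for prognosis.** With so few HFpEF patients, a bare percentage can mislead. A reported mortality of 0% is the plainest case.
- **The hospitalisation rate is not defined.** The number of admissions is verified, but section 7 gives no method for counts, repeat admissions or person-time. The percentage of patients admitted does not determine the number of admissions per patient-year.

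At stake is the use made of the result. Section 1.2 says of the study's data: "This will allow inferences to be made as to whether this population should be targeted for screening for HFpEF". A reader who took an unqualified percentage or p-value from about 15 patients as firm evidence on prognosis would be over-reading it.

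**Working it through.** **Inputs from section 7.** Prevalence 10%, half-width 5 percentage points, 95% confidence, drop-out 10%, sample sizes 139 and 155.

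**The plan's own figure.** n = 1.96² × 0.10 × 0.90 / 0.05² = 138.3, rounded up to 139. Then 139 / 0.90 = 154.4, rounded up to 155. Both reproduce.

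**Expected HFpEF patients.** 0.10 × 139 = 13.9 and 0.10 × 155 = 15.5, so about 14 to 16. The central 95% binomial ranges are 7 to 21 and 9 to 23.

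**Precision of a 12-month percentage.** The documents give no event rates, so the event counts are assumed. Exact (Clopper-Pearson) 95% intervals:

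| Events | Of 14 | Of 16 |
|---|---|---|
| 0 | 0 to 23% | 0 to 21% |
| 1 | 0.2 to 34% | 0.2 to 30% |
| 6 | 18 to 71% | 15 to 65% |

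The inputs to each interval are only the number of events and the number of patients. A frequency with its percentage supplies both, so the interval can be added at reporting without any further data.

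**Chance of seeing no HFpEF death.** With 14 patients and assumed 12-month mortality of 2%, 5% or 8%: 0.98¹⁴ = 0.75, 0.95¹⁴ = 0.49, 0.92¹⁴ = 0.31. A zero is quite possible, and the table shows how to report it.

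**What the log-rank test could show.** Assume HFpEF versus no HFpEF in a 10:90 split. By Schoenfeld's formula, 80% power at two-sided 5% needs (1.96 + 0.84)² / (0.10 × 0.90 × (ln HR)²) events: about 182 at a hazard ratio of 2 and 73 at 3. The first figure exceeds the whole sample of 155. With an assumed 20 events in all, power is about 15% and 31%. Naming the groups in advance would not alter this. Low power for a secondary aim is no error in a study sized for prevalence.

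**What the rate can mean.** The Study Summary attaches one word, rate, to both hospitalisation and mortality over 12 months. For mortality it is naturally the percentage dead by 12 months. Read in the same way for hospitalisation, it is the percentage admitted, which section 7 delivers. The two meanings do differ in size. If 40% are admitted at least once, the mean number of admissions per patient-year is:

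- Poisson: −ln(0.6) = 0.51
- negative binomial, k = 1: 1/0.6 − 1 = 0.67
- negative binomial, k = 0.5: 0.5 × (0.6⁻² − 1) = 0.89

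The spread matters only if admissions per patient-year are what is wanted. The documents nowhere mention person-time, and the dispersions here are assumed.

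**Censoring.** The 10% drop-out in section 7 inflates the sample for prevalence, which is measured at baseline. The documents do not say that it is loss during follow-up. Because section 3 verifies outcomes from records, a missed call need not mean a missing outcome. The time origin (enrolment) and the end (month 12) are both stated, and Kaplan-Meier estimation already handles any censoring that does occur.

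**The case for a change.** The strongest case for a change is that it is cheap. A few sentences would name the groups and events, define the rate and promise intervals, with no new visit or data item. Leaving the log-rank comparison open lets it be picked after the results are seen. A description based on about 14 patients also needs an interval more than most.

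Much of this stands. The three omissions are real, and analysts would do well to report exact intervals and to call any log-rank p-value descriptive. What does not follow is that the plan must be altered. Section 2.2 is about patients with HFpEF, all participants are followed, and the comparator is therefore the participants without HFpEF. A different grouping would be visible to any reader. The screening question in section 1.2 follows prevalence, the relation to sleep-disordered breathing and prognosis together; it rests largely on prevalence, and nothing makes it turn on a log-rank p-value.

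A fuller remedy would specify competing-risk estimates, special small-sample intervals under censoring and a negative binomial model for admissions. For about 14 patients the gain is doubtful. With an assumed 40% admitted and 8% mortality, allowing for death as a competing event moves the hospitalisation risk only from 40% to 38.5%. Any count model would rest on a dispersion that so few patients can hardly estimate.

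**Conclusion.** No change to the plan is needed. The unnamed groups and event, the undefined rate and the absent intervals are missing detail that a competent analyst fills sensibly. The methods that are stated give sound descriptive percentages and curves, and none produces a wrong answer.

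The imprecision is real: about 14 to 16 HFpEF patients, with exact 95% intervals from 0 to 21–23% when no event is seen to 18 to 71% for 6 of 14. It comes from the size of the study, not from the wording of section 7, and it can be shown at reporting from the same counts.

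This conclusion assumes 10% prevalence as in section 7, the percentage reading of the rate, and HFpEF versus no HFpEF as the comparison. If the investigators meant admissions per patient-year, they would have to choose a count method, but the verified admission counts would still be there to analyse.
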